5.6.2 Restricted Medications and/or Procedures

Patients will be advised to maintain their normal diet and avoid unhealthy levels of alcohol use or potassium-rich foods/drinks during the study period. See Section 8.12 for more details on monitoring of potassium and management of elevated serum potassium.

5.6.3 Documentation of Prior and Concomitant Medication Use

All medications in addition to the study drug (including vitamin preparations) that are taken by the patient during the study must be documented as concomitant medications and reported on the corresponding eCRF. The use of sodium bicarbonate or dosage adjustment for treatment of acidosis in CKD is permitted

Patients must currently be on 2 or more antihypertensive medications, which have been titrated upward as tolerated to recommended hypertension target doses (such as diuretics [except for potassium sparing diuretics], renin angiotensin system blockers, and/or calcium channel blockers. One of the antihypertensive medications must be high ceiling diuretic (loop or thiazide-like),

unless there is a documented intolerance or contraindication to diuretic therapy. The doses of the antihypertensive medications should be stable without dose adjustment during the 30 days prior to randomization. The dose of diuretic may be adjusted based on developing or resolved edema, weight gain or loss, or pulmonary congestion.

5.6.4 Management of Other Co-Morbidities

Patients who have additional co-morbidities (eg, diabetes, hyperlipidemia, and cardiovascular disease), should be managed and treated with glucose lowering, lipid lowering, and anti-platelet therapies as recommended by local clinical practice guidelines. It is highly recommended that any medical treatments for these co-morbidities will not be changed during the study period (from Screening to the End of Study Visit [Day 112]/Early Termination Visit).

6 STUDY PROCEDURES

6.1 Informed Consent

Written informed consent for the study will be obtained from all patients before any protocol-specific procedures are carried out.

6.2 Screening Visit (Visit 1)

The following procedures will be performed at Visit 1:

- Obtain informed consent:
- Assess eligibility criteria;
- Record demographics and medical history;
- Perform physical examination;
- Record height and weight;
- Calculate body mass index;
- Contact IRT;
- Perform 12-lead ECG in triplicate (patients should be resting in a supine position for at least 10 minutes prior to assessment);
- Obtain vital signs, including pulse rate, respiratory rate, and oral temperature;
- Obtain blood pressure;
 - Note: Patients must have uncontrolled hypertension, defined as resting trough-cuff seated SBP ≥ 140 and ≤ 179 mmHg, based on the mean of at least 2 current consecutive blood pressure readings in the clinic;
 - o Blood pressures are to be obtained according to the AHA recommendations for accurate blood pressure measurement. Patients should avoid smoking, caffeine, or exercise within 30 minutes before measurement; empty his or her bladder; then sit quietly in a comfortable chair with back support for at least 10 minutes before measurement and remain still during the measurement. The patient's limb should be supported to measure blood pressure to ensure that the blood pressure cuff is at heart level, using the correct cuff size. Do not take the measurement over clothes. Blood pressure measurements should be performed in the same arm throughout the study. Triplicate blood pressure measurements should be taken approximately 2 minutes apart with a validated, oscillometric upper arm blood pressure monitor. Trough cuff SBP and DBP values will be assessed based on the pre-defined blood pressure measurement guideline throughout the study. Pulse will be obtained simultaneously with blood pressure measurements;
- Obtain blood samples for:
 - o HIV, HbsAg, and HCV tests;
 - o Clinical laboratory tests (central laboratory; see Appendix B); and
 - o FSH (post-menopausal women only);

- Obtain urine sample for:
 - o Drug screen;
 - o Urinalysis (central laboratory; see Appendix B); and
 - O UACR:
- Obtain serum sample for potassium (local and central laboratories);
 - Note: Serum potassium should be $\leq 4.8 \text{ mmol/L}$ (local lab) to advance or continue to the placebo run-in Period;
- Obtain serum sample for creatinine (central laboratory);
- Obtain serum sample for pregnancy test (WOCBP only); and
- Record adverse events and concomitant medications.

If a patient is found to be not eligible during Screening, a single rescreening is allowed if the Investigator believes that the patient's condition has changed, and the patient may be eligible before the rescreening tests. Please note that a new patient number should be assigned to any rescreened patients, and all of the procedures defined in the protocol for the Screening Visit must be repeated.

6.3 Open-Label Placebo Run-In Period

6.3.1 Start of Open-Label Placebo Run-In Period (Visit 2)

The following procedures will be performed at Visit 2:

- Record weight;
- Contact IRT;
- Obtain vital signs, including pulse rate, respiratory rate, and oral temperature;
- Obtain blood pressure;
 - Note: Patients must have uncontrolled hypertension, defined as resting trough-cuff seated SBP ≥ 140 and ≤ 179 mmHg, based on the mean of at least 2 current consecutive blood pressure readings in the clinic;
 - o Blood pressures are to be obtained according to the AHA recommendations for accurate blood pressure measurement. Patients should avoid smoking, caffeine, or exercise within 30 minutes before measurement; empty his or her bladder; then sit quietly in a comfortable chair with back support for at least 10 minutes before measurement and remain still during the measurement. The patient's limb should be supported to measure blood pressure to ensure that the blood pressure cuff is at heart level, using the correct cuff size. Do not take the measurement over clothes. Blood pressure measurements should be performed in the same arm throughout the study. Triplicate blood pressure measurements should be taken approximately 2 minutes apart with a validated, oscillometric upper arm blood pressure monitor. Trough cuff SBP and DBP values will be assessed based on the pre-defined blood pressure measurement guideline throughout the study. Pulse will be obtained simultaneously with blood pressure measurements;

- Record adverse events and concomitant medications; and
- Instruct patient on study drug and dispense study drug.
 - o Note: Open-label placebo will be dispensed.

6.3.2 End of Open-Label Placebo Run-In Period (Visit 3)

The following procedures will be performed at Visit 3:

- Assess eligibility criteria;
- Check study drug accountability and collect unused study drug;
 - Note: If a patient's compliance to medications (including both open-label placebo and current antihypertensive medications) is < 80% or > 120%, he/she will not be eligible for the study and no further visits will be required;
- Record weight;
- Obtain vital signs, including pulse rate, respiratory rate, and oral temperature;
- Obtain blood pressure;
 - Note: Patients must have uncontrolled hypertension, defined as resting trough-cuff seated SBP ≥ 140 and ≤ 179 mmHg, based on the mean of at least 2 current consecutive blood pressure readings in the clinic;
 - o Blood pressures are to be obtained according to the AHA recommendations for accurate blood pressure measurement. Patients should avoid smoking, caffeine, or exercise within 30 minutes before measurement; empty his or her bladder; then sit quietly in a comfortable chair with back support for at least 10 minutes before measurement and remain still during the measurement. The patient's limb should be supported to measure blood pressure to ensure that the blood pressure cuff is at heart level, using the correct cuff size. Do not take the measurement over clothes. Blood pressure measurements should be performed in the same arm throughout the study. Triplicate blood pressure measurements should be taken approximately 2 minutes apart with a validated, oscillometric upper arm blood pressure monitor. Trough cuff SBP and DBP values will be assessed based on the pre-defined blood pressure measurement guideline throughout the study. Pulse will be obtained simultaneously with blood pressure measurements;
- Obtain urine sample for drug screen;
- Obtain serum sample for potassium (local and central laboratories);
 - O Note: Serum potassium should be $\leq 4.8 \text{ mmol/L}$ (local lab) to advance to randomization;
- Obtain serum sample for creatinine (central laboratory);
- Obtain blood sample for clinical chemistry (central laboratory; see Appendix B);
- Record adverse events and concomitant medications; and

• Instruct patient on 24-hour urine collection to be provided at Visit 4 and dispense laboratory materials for collection.

6.4 Randomization and Treatment

6.4.1 Day -1 (ABPM Visit)

This visit is for patients undergoing 24-hour ABPM only (a subset of up to 40 patients per treatment group who agree to participate in 24-hour ABPM and still meet eligibility criteria at the end of the run-in period [Visit 3]) and is to be scheduled within 3 days of the end of the run-in period (Visit 3).

The following procedure will be performed at the ABPM Visit:

• 24-hour ABPM device placement and start. Blood pressure and HR measurements will be obtained every 20 minutes during the interval of 06:00:00 hours to 21:59:59 hours (to coincide with the daytime, awake period) and every 30 minutes during the interval of 22:00:00 hours to 05:59:59 hours (to coincide with the nighttime, sleeping period). During the 24-hour ABPM recording period, a diary will be provided to the patient. Instructions and training will be provided to the site staff who will in turn provide instructions to the patient.

6.4.2 Day 1 (Visit 4) \pm 2 Days

This visit is to be scheduled within 4 ± 2 days after the end of the run-in period (Visit 3).

The following procedures will be performed at Visit 4:

- Assess eligibility: Patients must have uncontrolled hypertension, defined as resting trough-cuff seated SBP ≥ 140 and ≤ 179 mmHg, based on the mean of at least 2 current consecutive blood pressure readings in the clinic. Prior to randomization, all patients are to have a serum potassium ≤ 4.8 mmol/L at both Screening and the end of the placebo run-in period; and a mean (Visit 1 and Visit 3) eGFR ≥ 15 and ≤ 44 mL/min/1.73 m².
- Record weight;
- Perform physical examination (pre-dose);
- Perform 12-lead ECG in triplicate (patients should be resting in a supine position for at least 10 minutes prior to assessment);
- Obtain vital signs, including pulse rate, respiratory rate, and oral temperature;
- Obtain blood pressure prior to study drug administration;
 - O Blood pressures are to be obtained according to the AHA recommendations for accurate blood pressure measurement. Patients should avoid smoking, caffeine, or exercise within 30 minutes before measurement; empty his or her bladder; then sit quietly in a comfortable chair with back support for at least 10 minutes before measurement and remain still during the measurement. The patient's limb should be supported to measure blood pressure to ensure that the blood pressure cuff is at heart level, using the correct cuff size. Do not take the measurement over clothes. Blood pressure measurements should be performed in the same arm throughout the study. Triplicate blood pressure measurements should be taken approximately 2 minutes apart with a validated, oscillometric upper arm blood pressure

monitor. Trough cuff SBP and DBP values will be assessed based on the pre-defined blood pressure measurement guideline throughout the study. Pulse will be obtained simultaneously with blood pressure measurements;

- Obtain blood sample for clinical laboratory tests (central laboratory; see Appendix B);
- Obtain urine sample for:
 - o Urinalysis (central laboratory; see Appendix B);
 - o Urine pregnancy test for WOCBP only (pre-dose);
 - o UACR; and
 - o 24-hour urine for UACR;
- Obtain serum sample for potassium (local and central laboratories);
- Obtain serum sample for creatinine (central laboratory);
- Obtain plasma sample for PK from all patients (prior to patient's release from the unit);
- Obtain serum sample for aldosterone;
- Obtain plasma sample for renin;
- Obtain serum/plasma samples that will be stored at central laboratory for determination of various additional biomarkers, including but not limited to galectin-3, N-terminal of the prohormone brain natriuretic peptide (NT-proBNP), interleukin-6 (IL-6), collagen biomarkers, and C-reactive protein (CRP). The panel of biomarkers and time points for analysis will be determined prior to the database lock;
- Record adverse events and concomitant medications;
- After above laboratory and procedures, administer first dose of study drug and record time;
- Instruct patient on study drug and dispense study drug; and
- Download 24-hour ABPM readings at site (for a subset of up to 40 patients per treatment group who agree to participate in 24-hour ABPM and still meet eligibility criteria at the end of the run-in period [Visit 3] who undergo 24-hour ABPM).

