3 STUDY DESCRIPTION

3.1 Summary of Study Design

This is a Phase 2, randomized, double-blind, placebo-controlled, multi-center study to assess the efficacy, safety, and PK of KBP-5074 in patients with moderate-to-severe CKD and uncontrolled hypertension (Grade 1 to 2 systolic hypertension – ESC/ESH).

The study will enroll approximately 240 patients, randomized in a 1:1:1 ratio to 1 of 3 treatment groups (80 patients in each group): KBP-5074 0.25 mg QD, KBP-5074 0.5 mg QD, or placebo QD. Randomization will be stratified to balance enrollment for key variables that may influence safety and/or efficacy evaluations, including eGFR (\geq 30 versus < 30 mL/min/1.73 m²) and SBP (\geq 160 versus < 160 mmHg). Approximately 30% of patients enrolled in the study should have eGFR in the range of 15 to 29 mL/min/1.73 m². The study will be approximately 5 months in duration with 84 days of double-blind treatment.

The study will consist of up to a 4-week screening period, 2-week open-label (placebo) run-in period, 84-day double-blind treatment period, and a 4-week post-treatment safety follow-up period.

Plasma samples for PK analysis will be collected from all patients. A total of 4 PK samples will be collected from each patient, including at Day 1 (prior to discharge), Day 14 pre-dose, Day 28 pre-dose, and the End of Study Visit (Day 112)/Early Termination Visit. The pre-dose samples assume that patients will be dosed in the unit on the days above. If patients are not dosed in the unit on those days, a PK sample will be collected during each of these visits and the date and time of the last dose will be recorded.

Safety will be assessed systematically, and an independent data monitoring committee (IDMC) will perform cumulative reviews of safety data at regular intervals during the study.

Serum potassium levels, serum creatinine, and blood pressure will be closely monitored throughout the study and clinically significant changes will be reported as adverse events of special interest.

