- 12. Blood pressure and heart rate measurements will be obtained every 20 minutes during the interval of 06:00:00 hours to 21:59:59 hours (to coincide with the daytime, awake period), and every 30 minutes during the interval of 22:00:00 hours to 05:59:59 hours (to coincide with the nighttime, sleeping period). During the 24-hour ABPM recording period, a diary will be provided to the patient. Instructions and training will be provided to the site staff, who will in turn provide instructions to the patient.
- 13. If a patient has completed the 24-hour ABPM recording since their last visit, 24-hour ABPM data will be downloaded at the site during the ET Visit.
- 14. Clinical laboratories include chemistry, hematology, coagulation, and urinalysis. See Appendix B for the complete list of clinical laboratory analytes assessed for this study.
- 15. Only clinical chemistry will be conducted at the end of run-in period (Visit 3).
- 16. All patients must have a serum potassium ≤ 4.8 mmol/L at both Screening and the end of the placebo run-in period (Visit 3).
- 17. Serum pregnancy tests will be obtained at Screening, EOS, and ET. A urine pregnancy test will be obtained at pre-dose on Day 1.

- 18. Post-menopausal women only.
- 19. Serum/plasma samples taken during the study will be stored at a central laboratory for determination of various additional biomarkers, including but not limited to galectin-3, N-terminal of the prohormone brain natriuretic peptide, interleukin-6, collagen biomarkers, and C-reactive protein. The panel of biomarkers and time points for analysis will be determined prior to the database lock.
- 20. Plasma samples are to be collected prior to patient's discharge from the unit.
- 21. Plasma samples are to be collected pre-dose. If patients are not dosed in the unit on those days, a PK sample will be collected, and the date and time of the last dose will be recorded.
- 22. Open-label placebo will be dispensed at Visit 2.
- 23. The first dose of the study drug is to be administered.
- 24. The daily dose of the study drug is to be administered.
- 25. If a patient's compliance to medications (including both open-label placebo and current antihypertensive medications) is < 80% or > 120% at Visit 3, he/she will not be eligible for the study and no further visits will be performed.

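### Followed in order, Section 6.4.2 draws the Day 1 PK sample before any drug is given, at odds with its before-discharge timing elsewhere and leaving no sample scheduled near the peak

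*Combined protocol and SAP*

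**What the plan says.** Section 3.1, repeated in the synopsis, sets the PK schedule: "A total of 4 PK samples will be collected from each patient, including at Day 1 (prior to discharge), Day 14 pre-dose, Day 28 pre-dose". The fourth sample is at Day 112 or Early Termination.

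Section 6.4.2 (Day 1) has the line "Obtain plasma sample for PK from all patients (prior to patient's release from the unit". Several lines further down the same list comes the dosing instruction: "After above laboratory and procedures, administer first dose of study drug and record time".

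Appendix A gives the Day 1 sample its own footnote (20): "Plasma samples are to be collected prior to patient's discharge from the unit". Footnote 21, for Days 14 and 28, reads differently: "Plasma samples are to be collected pre-dose. If patients are not dosed in the unit on those days, a PK sample will be collected". For those two visits Section 3.1 adds that, when dosing is not in the unit, "a PK sample will be collected during each of these visits and the date and time of the last dose will be recorded".

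**The concern.** The dosing line in Section 6.4.2 is an explicit sequencing rule: everything above it comes first, and the PK draw is above it. The Day 7 and later visit lists only say to give the daily dose and note the time, with no such rule. A site that follows Day 1 literally collects a blank sample. The before-discharge label, set against pre-dose on Days 14 and 28, suggests that this was not intended.

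Population PK is a stated secondary objective (Section 2.2), and the exposure-response work in Section 9.2.4 builds on it. Section 5.2 reports AUC and Cmax up to around 60% higher in severe CKD and a possible link between exposure and hyperkalemia. Section 3.1 aims for about 30% of patients with eGFR of 15 to 29. Exposure is therefore worth characterising well here, and a missed Day 1 draw cannot be recovered later.

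**Working it through.** **Count.** The scheduled PK samples in Sections 3.1, 6.4.2, 6.4.4, 6.4.5 and 6.5 and Appendix A are Day 1, Day 14, Day 28 and Day 112 (or Early Termination). That is 4 per patient, which matches the plan's figure.

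**Exposure before Day 1.** The run-in is placebo only (Section 5.1) and patients from earlier KBP-5074 studies are excluded (Section 4.2, criterion 27). A draw before the first dose has an expected concentration of zero.

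**The four samples under each reading.**

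| Sample | In the order of 6.4.2 | Day 1 drawn after the dose |
|---|---|---|
| Day 1 | before any drug | after first dose, time not specified |
| Day 14 | trough, about 24 h | trough, about 24 h |
| Day 28 | trough, about 24 h | trough, about 24 h |
| Day 112 | about 28 days after last dose | about 28 days after last dose |
| Samples after at least one dose | 3 of 4 | 4 of 4 |
| Scheduled to fall at 4 to 7 h after a dose | 0 | at most 1, if the stay is long enough |

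The troughs are at about 24 h because dosing is once daily (Section 5.5.3). The 4 to 7 h time to peak comes from fasted healthy subjects (Section 1).

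**Size.** Active patients: 2 arms × 80 = 160. Planned samples from them: 160 × 4 = 640. Lost to the ordering: 160 × 1 = 160, and 160/640 = 25%.

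**How much Day 112 can add.** The documents give no half-life, so one is assumed over 12 to 96 h. The fraction remaining after t hours is 0.5^(t / half-life). At 28 days, t = 28 × 24 = 672 h:

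- 48 h: 0.5^14 = 0.006% (smaller still for shorter half-lives)
- 72 h: 0.5^9.33 = 0.16%
- 96 h: 0.5^7 = 0.78%

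The ±5-day visit window gives 23 to 33 days; at 96 h the range is then 1.9% to 0.33%. Day 112 probably adds little under either reading.

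**Cost of the ordering alone.** It is one sample per active patient: from 4 to 3 potentially informative samples if Day 112 is measurable, or from 3 to 2 if it is not.

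**Labels within 6.4.2.** The physical examination and urine pregnancy test are marked pre-dose, and blood pressure is marked as preceding study drug. The PK line instead carries a limit at release from the unit, which has a purpose mainly if the draw follows the dose. A draw before the dose is also before discharge, however, so a site could satisfy every written line and still collect a blank. No section says outright which side of the dose is meant.

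**The case against.** The strongest reply is that the specific label should outrank list position. The before-discharge timing appears in the synopsis, Section 3.1, Section 6.4.2 and footnote 20. The visit lists are not strictly chronological either: on Day 1, eligibility, which needs the blood pressure, is listed before blood pressure is taken, and Day 28 lists re-dispensing before the dose. This stands as evidence of intent. It does not remove the ambiguity, because the Day 1 list states an order in words.

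Two stronger readings are tempting, and the documents support neither.

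- A reader might infer that no post-dose sample would exist at all. Days 14 and 28 follow earlier daily doses, visits without dosing in the unit yield a sample at a known time since the last dose, and an Early Termination sample may follow recent dosing. What is missing is a sample scheduled in the absorption or peak phase.
- A reader might infer that absorption and volume could not be estimated. Section 9.2.4 leaves the model open, and Phase 1 PK data exist (Sections 1 and 5.2). Whether they would be pooled or used to fix parameters is not stated, so only the weaker statement is warranted.

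It is also fair to say that counting all patients (240 of 960 samples) overstates the loss, since the 80 placebo patients' samples contain no drug at any time. Finally, moving the line alone would not secure a peak sample: a patient released soon after dosing would still miss 4 to 7 h. That stands, and the fix addresses it.

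**Conclusion.** The point holds as an inconsistency with a real effect on data collection. Read in order, Section 6.4.2 makes 160 of 640 planned active-arm samples (25%) zeros and leaves two troughs and one late washout sample per active patient. Absorption and volume would then be poorly informed by this study's own samples.

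The 25% assumes 80 patients per active arm, a full schedule for each, and every site following the list literally; the true share depends on how sites read it. The view that Day 112 adds little rests on the assumed half-life range. The time to peak comes from fasted healthy subjects and may differ in these patients. Primary efficacy and safety analyses do not depend on any of this.

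**What to change.** Reconcile Section 6.4.2 with the synopsis, Section 3.1 and Appendix A footnote 20. Move the PK line in 6.4.2 below the first-dose line, worded along these lines: *after the first dose and before discharge; record draw time and dose time*. Put the same words in the other three places. Section 6.4.2 already asks for the dose time but does not mention the draw time.

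No time after dosing is given anywhere, so also state a target sampling window chosen with the 4 to 7 h time to peak in view, or say that varied times are accepted provided they are recorded. If a blank Day 1 sample was in fact intended, the text should say pre-dose and the PK section should acknowledge the loss.

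The cost is a wording change. The downside is that some patients wait in the unit after dosing, and longer if a window near the peak is chosen.
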